5.5.2 Visit 2 (day 1 after treatment ±2 days)

1. Question the Subject about AEs by asking an open-ended question taking care not to influence the Subject's answer, such as "Have you noticed any change in your health since the last visit, including any potential skin reaction in the treated anatomical area?". Record all events (including Local Skin Reaction), as appropriate on the corresponding CRF pages.
2. Enquire whether any concomitant therapies have been added, stopped, or changed since the subject's last visit. Document all changes in the CRF.
3. Collect the first subject questionnaire and ensure it is fully completed including the SIN and the treatment date. Report the subject's questionnaire in the eCRF.
4. Assess subject's compliance with regard to the study treatment. Based on the subject's questionnaire and discussion with the subject. Check the study treatment has been performed according to the provided instructions. Report the results in the eCRF.
5. Ensure that the subject has returned all used/unused investigational product.
 - a) Missing investigational product must be documented in the product dispensation log comments section and on other accountability form.
 - b) For all female subjects, reiterate the guidelines about contraception and risks in case of pregnancy.
6. Schedule the next follow up visit, week 12 (±7 days).

In case of early termination of the Clinical Trial for whatever reason:

- a) The subject will be fully evaluated.
- b) The procedures designated for the week 12 visit should be performed.

5.5.3 Week 12 / Last clinical trial visit or Early trial termination visit

1. Question the Subject about AEs by asking an open-ended question taking care not to influence the Subject's answer, such as "Have you noticed any change in your health since the last visit, including any potential skin reaction in the treated anatomical area?". Record all events (including Local Skin Reaction), as appropriate on the corresponding CRF pages.
2. Enquire whether any concomitant therapies have been added, stopped, or changed since the subject's last visit. Document all changes in the CRF.
3. Using the transparent sheet which was completed at Baseline, relocate the anatomical area defined at baseline and each treated AK lesion. Assess the lesion response for each treated AK mapped at Baseline (see Sections 7.2.1 and 7.2.1.2). Identify new lesions.

Note: Any lesion in the anatomical area identified at Week 12 but not at Baseline is defined as a new lesion. Total number of new lesions should be recorded in the eCRF.

4. On each AK lesion that has completely responded, perform Investigator Clinical Assessment of the subject's Skin Aspect (see [7.2.2](#)).
5. Assess the skin photodamage of the selected anatomical area using the Dover's modified global photodamage score (see [7.4.1](#)).
6. Conduct a pregnancy test on any female of childbearing potential. In case of positive result, please refer to Section [8.3](#).
7. *For selected sites only*, take photographs of anatomical area according to the provided procedure only if subject has agreed on the approved Photo release consent form.
8. Ask the subject to fill out the subject week 12 questionnaire and collect it. Ensure it is fully completed and with SIN number. Report the week 12 questionnaire in the eCRF.
9. Complete CRF Exit form and discharge Subject from the study.
10. Physician questionnaire should be completed once all subjects from the site have completed the study

At a minimum, the tasks numbered 3, 4, 5, and 9 have to be performed by a Dermatologist.

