7 STUDY ASSESSMENTS

Clinical evaluations should be performed by the same investigator throughout the clinical trial.

If it is not possible to use the same investigator to follow a subject, then evaluations should overlap for at least one visit in order to examine the subject together and discuss findings. This should be documented in medical source documents.

7.1 Subject Reported Outcomes (PRO):

The day of treatment after daylight exposure and at Week 12/Early termination, subjects will complete a questionnaire regarding the treatment procedure (skin preparation, study product application, weather condition daylight exposure, skin discomfort, efficacy, overall satisfaction, etc.) (Appendices 1 & 2).

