7.5 Appropriateness of measurements

All measurements planned in this study are non-invasive.

PRO will be evaluated using a questionnaire after treatment and at the end of the study. Treatment compliance will be evaluated based on the recording of treatment information on the subject questionnaire. The questionnaire will collect specifically information on the treatment

procedure, the subject's opinion on the treatments and on the associated cosmetics products used in the trial.

Efficacy will be evaluated by assessing the lesion response which is a sensitive endpoint widely used in clinical practice to assess cure of AKs. At the Week 12 visit, the Investigator will identify all AK lesions (new or initial) on the anatomical area and will define, for each lesion pre-existing at Baseline, the lesion response as CR or non-CR (see [7.2.1.2](#)). This will allow determining the number and percentage of cured lesions.

The safety of investigational product will be assessed through the reported AEs. To complete safety assessment, the Subject's pain assessment after treatment and Subject's skin aspect at Week 12 will also be measured.

The same investigator will evaluate the same subject at each visit throughout the clinical trial.

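### The week 12 satisfaction questionnaire is listed after the dermatologist's examination, and no visible passage makes the subject answer first

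*Combined protocol and SAP*

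**What the plan says.** Section 5.5.3 gives a numbered list of ten tasks for the week 12 or early termination visit. The ones that matter here are:

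- Item 1, adverse events: "Question the Subject about AEs by asking an open-ended question taking care not to influence" the answer.
- Item 3, lesion response and new lesions: "Assess the lesion response for each treated AK mapped at Baseline".
- Item 4, skin aspect: "On each AK lesion that has completely responded, perform Investigator Clinical Assessment".
- Item 5, photodamage: "Assess the skin photodamage of the selected anatomical area using the" modified Dover score.
- Item 8, the subject's form: "Ask the subject to fill out the subject week 12 questionnaire and collect it. Ensure it is fully completed and with SIN number".

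The list closes with a staffing rule: "At a minimum, the tasks numbered 3, 4, 5, and 9 have to be performed by a Dermatologist". The questionnaire is therefore not reserved for a dermatologist; the examinations before it are.

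Elsewhere the timing of the form is given only by visit. Section 7.1 says "The day of treatment after daylight exposure and at Week 12/Early termination, subjects will complete a questionnaire regarding the treatment procedure", and section 7.5 says "PRO will be evaluated using a questionnaire after treatment and at the end of the study". Footnote e of the flow chart (5.4) and the Appendix 2 instructions likewise give a visit or a time since treatment, not a place within the visit.

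**The concern.** Section 3.1 makes subject-reported satisfaction at 12 weeks the objective. An answer about how well lesions cleared, or how the skin looks, is best taken before a clinician has examined those same features in front of the subject. Once the examination has taken place, the answer can pick up what the clinician said, did or seemed to think.

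The route is plausible here. Complete response is judged by touch as well as by sight (7.2.1.2), and the area may be the scalp, so the examination can bring out things the subject had not noticed. Lesions that remain or are new may be treated at the same visit (4.3.5 and the part of 7.2.1 on new lesions). An offer of such treatment would tell the subject that clearance was incomplete.

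The protocol protects other subject reports more closely. The adverse event question has its own wording against influence. The pain score is kept apart from analgesics (5.6) and moisturizer (6.2), and Appendix 1 is to be completed as soon as the daylight exposure ends. The week 12 form has no comparable rule about when in the visit it is filled out.

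**Working it through.** The point concerns order within a visit, so most of the check is a comparison of passages.

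**1. The plan's own figure.** Section 9.2.2 gives a precision of 10% for 85% satisfaction in 50 subjects. Assuming a two-sided 95% normal interval (the confidence level is not stated), the half-width is 1.96 × √(0.85 × 0.15 / 50) = 0.099. The figure reproduces. It covers sampling error only, so it neither depends on the order of the visit nor allows for an effect of it.

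**2. Overlap between form and examination.** Appendix 2 has 9 questions. Three use the satisfaction scale:

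| Appendix 2 question | Subject matter | Examined in 5.5.3 |
|---|---|---|
| Q1 | Clearance of AKs | Item 3 |
| Q3 | Skin aspect of the treated area | Item 4 |
| Q8 | Overall: procedure, effectiveness, side effects, skin aspect | Items 3 and 4, for 2 of the 4 named parts |

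So 3 of the 3 satisfaction ratings concern matters examined earlier in the list. This counts overlap in topic; it does not count altered answers.

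**3. Is there a rule that the subject answers first?** The flow chart and its footnote e, sections 7.1 and 7.5, and the Appendix 2 instructions contain none. The one passage that places an action after completion of a subject questionnaire (4.3.5) concerns cryotherapy outside the treated area at baseline, and its purpose is to protect the pain score. For treatment of lesions at the last visit, 4.3.5 refers to the clinical assessments and does not mention the questionnaire.

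**4. Is the list a binding sequence?** It is not declared to be one, and item 10 (the physician questionnaire, completed once all of a site's subjects have finished) cannot belong to a sequence within a single visit. That leaves two readings:

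- Sites follow the numbering. The order is then uniform, and every week 12 form comes after the examination.
- Sites do not. The order is then left to each site and may differ between them. With 5 to 10 subjects planned per site (5.1), one site's order would govern 5/50 = 10% to 10/50 = 20% of the planned subjects. That is the share of forms collected under one order, not the share of answers changed.

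These readings are alternatives, and neither protects the week 12 answers.

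**5. What is unaffected.** Appendix 1, including its satisfaction question Q19, is completed on the treatment day, away from any examination.

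**The case against.** The strongest reply is that the protocol is silent rather than wrong. The numbered lists are loose: in the baseline list (5.5.1) eligibility is checked at item 5, but the lesion count that eligibility needs comes at item 10. Where the protocol wants an order it says so in words. On this view, being item 8 proves little. This stands in part, and it is why the point is put as two alternatives. But sites are given this list as the description of the visit, and following it as written puts the form after the examination.

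Second, the Appendix 2 preamble tells subjects that no answer is right or wrong and that their future care will not be affected. That is real care against influence, but it does not address what the subject has just seen or heard. Subjects can also judge their own skin, which argues for recording their own view first.

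Third, satisfaction informed by the examination could be a legitimate target. No passage says that it is the intended one, and if it were, the order would still need to be fixed.

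Three stronger readings are tempting, and the documents do not support them:

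- A reader might infer that the satisfaction results are biased, presumably upwards. No passage describes findings being disclosed before the form is completed, and incomplete clearance could just as well lower the ratings.
- A reader might infer that answers are both affected by the examination and collected in varying order. If the list is followed there is no variation from this source; if it is not, the list is no evidence that the form comes last.
- A reader might infer that nothing could be done later, because 9.1.3 presents tables by treatment and visit. Section 9.1 leaves the detailed analysis to a separate SAP, and 10.1 mentions a trial reference manual meant to standardise assessments. Neither is visible, and either may address the point.

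**Conclusion.** The point holds as a weakness of design in section 5.5.3. The listed order places the 12-week satisfaction questionnaire after an examination of the same matters, and no visible passage requires the subject to answer first. It reaches all three satisfaction ratings in Appendix 2, which serve the trial's objective. The size and direction of any effect cannot be derived from the documents, and it may be zero.

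The conclusion assumes that sites either use the list as their working order or choose their own, and that neither the reference manual nor the separate SAP settles the matter. The trial is descriptive and calls itself exploratory, so no test result is at stake. What is at stake is how the main descriptive result can be read. The change is worth making because it costs very little and protects the stated objective.

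**What to change.** In 5.5.3, move the questionnaire to after items 1 and 2 and before the lesion assessment. Keeping it after item 1 matters because Appendix 2 Q2 and Q4 ask about side effects and skin reactions and would otherwise prime the open adverse event question. Add two statements:

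- The subject completes the form before any lesion examination or discussion of findings.
- The dermatologist does not see the answers until lesion response, new lesions, skin aspect and photodamage have been recorded.

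The second statement is needed because the assessor is unblinded and should not grade lesions knowing how satisfied the subject is. Existing site staff can hand out and check the form, since it is not a task reserved for a dermatologist. Once the item has moved, the closing line on dermatologist tasks must be renumbered from 3, 4, 5 and 9 to 4, 5, 6 and 9.

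The new order applies at early termination without further edits, because 4.4 and 5.5.2 refer to the week 12 procedures. The cost is one moved item, two sentences and the renumbering, with no extra visit, staff or procedure and no change to the 50 planned subjects. The small downside is that the form must be given before the examination and kept from the assessor until grading is recorded.

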5.6 Subject instructions

At baseline, subject will be requested to comply with the treatment procedure instructions. After having trained the subject, the investigator will provide him/her with the written study treatment instruction sheet including storage conditions.

Throughout the study, Subject will be requested to comply with the following:

1. To avoid the use of antalgics the day of treatment and the day before treatment until the subject self-assessment of pain is complete.
2. To avoid Sun exposure of treated anatomical area and use sunscreen during the 2 days following the treatment.
3. To apply a moisturizer in case signs of local skin irritation such as dryness or erythema are observed after the PDT procedure. The subject will be instructed that the use of a moisturizer should be considered only after the study treatment and when self-assessment of pain is performed.
4. To respect the visit timeframe.
5. In case the subject is using forbidden topical therapy listed in exclusion criterion (Section [4.2.2](#)) or any other treatment on an area other than the anatomical area, the Investigator will remind him/her to pay a strict attention to not apply any of these therapies on the anatomical area.

Please refer to Section 4.2.1 and Section 4.2.2 for other items linked to eligibility criteria.

6 CLINICAL SUPPLIES

Investigational product and supplies will be provided by the sponsor and shipped by the clinical supply unit to each investigator site. The investigational product used during this clinical trial is marketed product.

6.1 Investigational product identification and use

6.1.1 Product identity

	Investigational Product
Trade Name	Luxerm®
Name of Active Ingredient	methyl aminolevulinate hydrochloride
Pharmaceutical Form	Cream
Dose or Concentration	160 mg/g
Formula number	0401
Total Daily dose	Thin layer on field area of either face or scalp
Mode and frequency of administration	Topical, single dose
Duration of administration	2 hours and 30 minutes
Location of treated area	Face or scalp
Manufacturer (Name and address)	Laboratoires Galderma [name]
Packaging type and size (primary)	2g collapsible aluminium white tubes
Storage Conditions	Between 2 to 8 °Celsius

6.1.2 Method of treatment assignment

This study is an open study without randomization. Indeed there is no treatment assignment, the investigational product will be provided in bulk.

A tracking of the investigational products used will be done by recording the dispensation in the investigational product dispensation log.

6.1.3 Subject Identification Number (SIN)

Upon signature of the informed consent, a subject meeting all inclusion/exclusion criteria will be allocated a unique Subject Identification Number at baseline automatically generated by the eCRF.

During the whole clinical trial, the subject will only be identified using the SIN for all documentation and discussion.

6.1.4 Instructions for use and administration

At baseline visit the investigator or designee will give each subject verbal and written instructions on how to use the investigational and non-investigational products. It will be confirmed to treat the selected AKs anatomical area on the face excluding nose (e.g., forehead or cheek or chin), or balding scalp (excluding eyelids, lips and mucosa) with field therapy by providing the subject with the study treatment and by explaining in details the procedure.

Table 2: Procedures for Luxerm® DL-PDT treatment

Baseline Visit 1	Anatomical area and lesion mapping by the investigator using a transparent plastic sheet (after confirmation that all inclusion criteria and none of the exclusion criteria are met). Removal of any scales and crusts in the anatomical area by the investigator if deemed necessary.	
	Subject provided with oral and written instructions on the treatment procedure of the anatomical area (lesions and field). The patient should undergo treatment at home in the following week (\pm 7 days), with appropriate weather conditions, as follow:	
Treatment day*	t -15 min	The subject applies Actinica sunscreen on the selected anatomical area and all other sun exposed skin. The quantity of sunscreen will be sufficient to cover all areas exposed during the DL exposure step.
	t=0 min	After approximately 15 min once the sunscreen (Actinica sunscreen) has dried, the subject prepares the anatomical area to be treated with an abrasive pad to remove scales and crusts and roughen the surface of the lesions
	t=30 min	Then, the subject applies a thin layer of Luxerm® on the entire anatomical area using the provided finger glove and avoiding contact with eyes, lips and mucous membranes.
	t=2h30	The subject goes outdoors no later than 30mins of application of Luxerm® for 2 hours daylight exposure. On sunny days, should the subject feel uncomfortable in direct sunlight, shelter in the shade may be taken.
		The subject returns indoors and Luxerm® is removed by washing

* Subject will be advised to follow the instructions as close to the baseline visit (within 1 week \pm 7 days) with appropriate weather condition to ensure the instructions are well followed.

As a general precaution, sun exposure of the treated anatomical area should be avoided for about 2 days following treatment. Subjects are advised to use a sunscreen in all exposed areas, including the treated area, during this period

At 1 week post-baseline the investigator will call the subject to check if the study treatment has been performed:

If the subject was not able to perform the study treatment during the week post-baseline due to bad weather conditions, another additional period of maximum 7 days is offered to perform the study treatment.

For an additional period greater than 7 days the decision to maintain the subject in the study will be based on discussion between PI and sponsor.

If the subject decides to stop his participation for whatever reason, he/she will be asked to return the study product to the site. Appropriate treatment will be decided at investigator discretion. The study product must not be reallocated to another subject and should be discarded from the study product stock. Investigator has the possibility to replace the subject.

6.2 Other supplies

Galderma will provide the sites with:

- The Urinary Pregnancy Tests (UPT) that may detect urinary Human Chorionic Gonadotropin concentrations equal to or greater than 25 international unit)
- Cetaphil moisturizer cream
- Actinica Sunscreen SPF 50+
- Nitril finger gloves for Luxerm® cream application
- An abrasive pad for skin preparation
- Cool bag for Luxerm® cream transportation

No specific labels will be used.

No accountability will be conducted on these products.

The provided sunscreen has been selected so as not to prevent the transmission of light wavelengths required for activation of PpIX and to offer an adequate sun protection for the 2-hour duration of the DL exposure. The provided sunscreen will be used only for the treatment preparation and will be applied if any sun exposure is expected following the treatment.

Cetaphil moisturizer cream will be used on the whole anatomical area at night for 8 days after treatment. It is provided in case of occurrence of phototoxicity reaction on the anatomical area treated (burning sensation, prickling or tingling skin, irritation such as dryness, redness, edema or crusts) after the daylight exposure or soon after, requiring the use of moisturizer. **Moisturizer application should not be done before the treatment procedure or before the Subject Self-assessment of Pain is completed.**

6.3 Investigational product packaging and labeling

Each Luxerm® tube will be supplied with single label. Label on secondary packaging (box) will comprise affixed and tear-off portions.

For treatment documentation, the affixed portion of the label will remain on the appropriate box. The tear-off portion of the label is to be removed at the time of dispensation and affixed to the product dispensation log.

The label (including tear-off part) will be printed in German and will contain information required by Good Manufacturing Practice (GMP) and local regulations and will be printed in local language.

6.4 Investigational product management

6.4.1 Accountability

Upon receipt of the clinical supplies at the site, the investigational product dispenser will conduct a complete inventory of all investigational products and assume responsibility for their storage, accountability and dispensation.

The Investigator or designee will sign the original Acknowledgement of receipt form upon receipt and inspection of the supplies, fax the signed copy to *GALDERMA R&D* and retain the receipt in the Investigator Site File (ISF).

All supplies sent to the investigator site will be accounted for and in no case used in any unauthorized situation.

At the end of the trial, all used and unused investigational product will be appropriately inventoried by the monitor and will be returned to *GALDERMA R&D* for further reconciliation, appropriate inventory and destruction.

6.4.2 Dispensing

All investigational products will be prescribed only to subjects enrolled into the clinical trial, at no cost and in accordance with the conditions specified in the protocol.

Dispensation will be appropriately documented on the product dispensation log by the investigational product dispenser at each visit.

Each subject will receive 1 tube of Luxerm® 2g at Baseline.

